APPENDIX A

Study Rationale Product Selection Justification

RATIONALE FOR STUDY

1. Introduction

This document is designed to provide relevant information and rationale for the conduct of the subject study. Prior to initiation of protocol development, an effort was made to check for existing data that could be utilized / substituted to estimate exposure from use of antimicrobial aerosol products both in household and commercial/institutional settings. Additionally, the information collected would also provide a valuable tool in selection of the product/s and study design for estimating exposure from use of pressurized aerosol cans.

2. Literature Review

A literature search revealed that very little data existed on exposure to pressurized aerosol products. The most relevant articles were selected and a summary of those reports/publications is provided as part of the justification for the conduct of the subject study and its application in the proposed study design and product selection.

2.1. Berger-Preiss et al. (2005):

This study was conducted in response to the EU Directive 98/8/EC, to estimate inhalation and dermal exposure during spray applications of biocides. The study involved an extensive survey of published and unpublished literature regarding use of biocides and categorized the information according to the uses e.g., greenhouses, indoor pest control, stables, wood preservatives and antifouling agents. Measurements were performed at selected workplaces during disinfection operations in food and feed areas; pest control operations for private, public and veterinary hygiene; wood preservative and anti-fouling agents. In order to compare literature results regarding influence of parameters relevant to exposure (e.g., spraying equipment, nozzle size, direction of application), model experiments were conducted in 60 m³ rooms. The sprayers used in the model experiment were Frowein "Spray Boss" with various nozzle sizes (low pressure); Wagner (airless sprayer); and a cold fogging apparatus which represented the range of equipment used in the work place. In the extensive literature survey conducted by the authors, only one reference regarding use of aerosol cans for indoor and/or green house pest control was available.

The research literature survey of work place measurements were mostly related to agrochemicals, wood protection, and paint with high or low pressure aerosol generation. The inhalation exposure monitoring data was mostly from green houses, including re-entry type of studies for worker safety using stationary sampling or personal pumps. The results from work place measurements and model experiments revealed the following:

- Particle size distribution was the most important parameter and was dependent on the nozzle size of the sprayer
- Fine particles stayed suspended longer and gave higher inhalation exposure
- Inhalation exposure was lowest when spraying direction was downward
- Inhalation exposures was higher during overhead spraying
- Highest inhaled dose rates were measured during fogging
- Sprayers' distance from the sprayed object was of minor importance

- Higher pressure spraying led to higher exposure
- Spraying of higher application volumes (amount of active material) per time led to an increased inhalation exposure
- Air concentrations were higher without ventilation
- Dermal exposures were very much dependent on the spraying direction and apparatus
- Spraying the upper part of the wall, the head, upper arms and thighs had most exposure (with Spray Boss) and exposure was lower during fogging and horizontal spraying and also lower during spraying of the lower part of the wall
- Dermal exposures varied by a factor of 10 and were dependent on the behavior of the user
- Model experiments were predictive of the field measurements
- Aqueous solutions gave higher concentrations compared to higher vapor pressure solvent based solutions
- No major differences between stationary sampling or personal pumps, with slightly higher trend with the personal pump

The study does not provide exposure data which is directly applicable to the cleaning and disinfecting aerosol products in cans represented by the Task Force membership. However, the study provides useful information in selecting the product/s and in study design. Based on this information one can conclude that a product which will have a higher number of particles in the inhalable range (fine spray), used in multi-directional orientation, in confined spaces and with relatively low vapor pressure will provide the greatest exposure.

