4.2 Products Selected for the Pilot Study

The following products with active ingredients were selected:

- 1. Hard surface disinfectant fine spray (Nozzle 0.02"; Release rate 1.36 g/s)
 - Clorox Disinfecting Spray (DDAC, ADBAC, ODAC, DODAC, Ethanol)
- 2. Foaming aerosol product (Nozzle 0.016"; Release rate 1.8-2.4 g/s)

Antibacterial Scrubbing Bubbles Bathroom Cleaner (ADBAC)

3. Soft surface disinfectant (Nozzle 0.02"; Release rate 1.1-1.6 g/s)

Lysol Brand Disinfectant Spray (ADBAS, Ethanol)

4. Air freshener (Nozzle 0.03"; Release rate 1.3 g/s)

Stepan Aerosol SDAS (ADBAC)

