All products except the air freshener were sprayed against a hard surface for 10 seconds from a distance of 6 inches and height of about 5 feet at three different location in the in the room (three replicates). The air freshener was applied in the air at about 6 feet height. For each replicate (Spray location) samples for air concentration were taken concurrently using both OVS and IOM tubes (for comparison and subsequent selection). The IOM and OVS tubes are commonly used for collecting both volatiles and particulate matter in the breathing zone. Particle size distribution was determined using a RespiCon 3-stage Impactor with particle size cuts at 2.5, 10.0 and 100 µm (RespiConTM Particle Sampler - Model 8522, TSI Inc.). Samples were collected by placing sampling tubes/samplers on a laboratory stand at about five feet height representing the breathing zone and position of the user. The sampling tubes/samplers were placed facing the wall where test material was applied, again simulating the exposure position of the user. For the air freshener the sampling stand was placed under the area where test substance was applied. The amount sprayed per unit time (10 seconds) was determined from four to five replicates per product by weight difference of the aerosol cans before and after application. All samples were collected using personal air pumps drawing 2 L/min and 3.2 L/min, for IOM/OVS and Respicon, respectively. All samples were analyzed for C14 ADBAC, the active ingredient (AI) common in the selected products using HPLC MS/MS. The environmental chamber was vented prior to each product use.

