The results of the pilot study clearly show that based on nozzle size, amount of material dispensed per unit time, air concentrations, and aerosol characteristics, the hard surface disinfectant product, i.e., Clorox Disinfecting Spray (EPA Reg. No. 67619-03), represents the high-end exposure scenario and the product most likely to produce measurable exposure and would therefore serve as the surrogate for the study entitled "Measurement of Potential Dermal and Inhalation Exposure During Application of a Liquid Antimicrobial Pesticide Product Using a Pressurized Aerosol Can for Indoor Uses". Taking type of surface and the inspirable mass into consideration, the Clorox Disinfecting Spray (hard surface fine Spray) and Stepan Aerosol SDAS (Air Freshener) represent uses with the most inhalation and/or dermal exposure potential. The Air Freshener seemed to have comparable inspirable mass to the hard surface spray. However, as mentioned previously, the total mass of the active ingredient dispensed per unit time for the Clorox Disinfecting Spray is more than double the Stepan Aerosol SDAS (17.2/6.7 mg, Table 4) and dermal exposure will likely be higher for the Clorox Disinfecting Spray. Additionally, the hard surface spray product will be used to a much greater extent in a day, especially in commercial use, than the air freshener. Based on the available data, the Clorox Disinfecting Spray (hard surface fine spray) would represent a high end conservative choice for exposure monitoring studies.

The selected product would also meet objectives of the study and test material selection criteria, i.e.:

- Serve as surrogate for most aerosol use categories
- Use pattern represents high end exposure a conservative scenario
- Use scenario covers most influential variables of exposure
 - o Highest % of AI
 - o Nozzle size of majority of the aerosol products
 - o Particle size distribution representative of fine spray
 - Used for hard surface and confined spaces
- Having stable active ingredient
- Results can be extrapolated to most products on the market

6. References

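### The test product is called conservative, but this is not shown for inhalation exposure per unit of active ingredient, and the pilot's own figures leave under-prediction open

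*Combined protocol and SAP*

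**What the plan says.** Appendix A, Section 2.1 summarises a published study of biocide spraying. One of its findings reads "Aqueous solutions gave higher concentrations compared to higher vapor pressure solvent based solutions". The section concludes that a product with more fine particles, "used in multi-directional orientation, in confined spaces and with relatively low vapor pressure will provide the greatest exposure", and says the study helps in choosing the product.

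The list of influential variables (Appendix A, 2.6.1), the selection criteria (3.0) and the closing criteria (5) name neither vapour pressure nor solvent base. Section 2 of the rationale mentions volatility only for the active ingredient.

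Appendix A, Section 4.2 gives the actives of the four pilot products (closing brackets cut): "Clorox Disinfecting Spray (DDAC, ADBAC, ODAC, DODAC, Ethanol" (the test product), "Lysol Brand Disinfectant Spray (ADBAS, Ethanol", "Antibacterial Scrubbing Bubbles Bathroom Cleaner (ADBAC" (a foam) and "Stepan Aerosol SDAS (ADBAC" (the air freshener, a fine spray in Table 1). Section 4.3 adds: "All products except the air freshener were sprayed against a hard surface for 10 seconds". The air freshener was sprayed into the air.

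Appendix A, Section 5 calls the test product a high-end, conservative choice and says "Results can be extrapolated to most products on the market". Section 5.4 of the rationale foresees no important source of underestimation.

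**The concern.** Two things do not fit together.

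First, a determinant that the plan's own review identified drops out of the visible selection argument without explanation. The chosen product lists a volatile solvent, and the pilot has no hard-surface fine spray without listed ethanol to compare it with.

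Second, the main case for conservatism is on the wrong scale. It rests on the test product having the highest percentage of active and dispensing the most active per unit time. The air freshener is set aside because it dispenses less and is used less. But Section 4 of the rationale extrapolates by proportionality, E2 = H2(E1/H1), and Section 6.1 works with exposure normalised to active handled. On that scale concentration and amount used divide out. What remains is the fraction of the active that becomes and stays airborne. A product that is high-end in absolute terms need not be high-end per unit of active.

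If another product type puts a larger fraction into the air, the database would under-predict its inhalation exposure. Every monitoring event uses one formulation, so more events could not reveal this. Section 5.4 treats overestimation as harmless because it is protective; this error could run the other way.

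**Working it through.** **Inputs.** Appendix A Table 4 (mean g dispensed in 10 s, C14 ADBAC fraction), Table 5 (OVS and IOM residue, three replicates, geometric means) and Table 6 (Respicon total).

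**Step 1: reproduce Table 4.** mg ADBAC = mean g × fraction × 1000, from the unrounded means of the listed cans.

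- Test product: 13.625 × 0.00126 × 1000 = 17.17 (stated 17.2)
- Foam: 18.8 × 0.00066 × 1000 = 12.41 (stated 12.4)
- Lysol spray: 12.625 × 0.00053 × 1000 = 6.69 (stated 6.7)
- Air freshener: 13.02 × 0.0006 × 1000 = 7.81 (stated 7.8)

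All agree within 0.2%. The Table 5 OVS geometric means also reproduce (925, 87, 48 and 905 ng).

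**Step 2: put air residue on the plan's scale.** Residue per mg = ng collected ÷ stated mg ADBAC dispensed, using unrounded geometric means for OVS and IOM.

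| Product | Ethanol listed | Target | OVS ng/mg | IOM ng/mg | Respicon total ng/mg |
|---|---|---|---|---|---|
| Test product | yes | wall | 925/17.2 = 53.8 | 994/17.2 = 57.8 | 640/17.2 = 37.2 |
| Lysol spray | yes | wall | 48/6.7 = 7.2 | 49/6.7 = 7.3 | 43/6.7 = 6.4 |
| Foam | no | wall | 87/12.4 = 7.0 | 97/12.4 = 7.8 | 109/12.4 = 8.8 |
| Air freshener | no | air | 905/7.8 = 116.1 | 860/7.8 = 110.3 | 987/7.8 = 126.5 |

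**Step 3: ratio of air freshener to test product.**

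- Unadjusted: OVS 905/925 = 0.98; IOM 860/994 = 0.87; Respicon 987/640 = 1.54.
- Per mg dispensed: OVS 116.1/53.8 = 2.2; IOM 110.3/57.8 = 1.9; Respicon 126.5/37.2 = 3.4.

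The unadjusted OVS and IOM residues are similar, but the test product needed 17.2/7.8 = 2.2 times as much active to produce them. Appendix A, Section 5 presents this larger dispensed mass as a margin of safety (it prints 17.2/6.7, which uses the Lysol value). On the normalised scale it is no margin.

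**Step 4: how firm is the ratio?** The air freshener's five cans ran from 4.9 to 22.5 g, that is 2.94 to 13.5 mg ADBAC.

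- OVS ratio: (905/13.5)/53.8 = 1.2 to (905/2.94)/53.8 = 5.7.
- Respicon ratio: (987/13.5)/37.2 = 2.0 to (987/2.94)/37.2 = 9.0.

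The IOM replicates overlap: the test product's highest is 1652/17.2 = 96.0 ng/mg and the air freshener's lowest is 692/7.8 = 88.7 ng/mg.

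**Step 5: does listed ethanol order the products?** No. The two ethanol-listing sprays differ 53.8/7.2 = 7.5-fold by OVS, and the foam, with none listed, matches the lower of them.

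**The case against.** The strongest reply is that nothing here isolates a solvent effect. The air freshener differed from the test product in spray target (air against wall), sampler position (under the spray against facing the wall), nozzle (0.03 against 0.02 inch) and steadiness of output. There were three replicates. This stands in full, so the ratios cannot be attributed to vapour pressure.

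The reviewed study used other spraying equipment, and Appendix A says its data do not apply directly to canned products. It names particle size as the most important parameter, and the plan did carry that forward: among hard-surface fine sprays the test product had the lowest particle sizes. In the pilot it also gave the most residue per mg of the three wall-sprayed products. This supports conservatism against those two products. It does not reach air-treatment products, whose particle sizes extend lower (16-87 µm) and which Section 2 includes in the scenario.

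A reader might infer that the product under-predicts exposure for ethanol-free sprays, or that results should be confined to ethanol-containing ones. The documents support neither. They list actives only and give no solvent composition or vapour pressure, so absence of ethanol from a list does not establish an ethanol-free formulation. Two of the four pilot products list none, and listed ethanol does not order the results (Step 5).

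Table 3 and some text before the pilot objectives are missing from the copy reviewed, so solvent may be discussed there. The point about normalisation does not depend on that.

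**Conclusion.** The point holds as a gap in support, not as a demonstrated bias. For inhalation exposure per unit of active handled, the claims that the product is conservative, that results extend to most products and that no significant underestimation is foreseen have not been shown. The one fine spray in the pilot without listed ethanol, tested only in air, gave about 1.9 to 3.4 times the test product's airborne ADBAC per mg dispensed, depending on the sampler.

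This rests on the plan's own proportionality principle and on Table 4 mean output as the denominator; Step 4 shows how far can-to-can variation moves the ratios. It concerns inhalation only, since the pilot did not measure dermal deposition.

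A reader might also want to turn an assumed multiplier into a loss of the 3-fold accuracy benchmark. The documents give no such multiplier, the planning GSD in Section 6.3 comes from dermal data, and the benchmark describes sampling accuracy under the reference model, not transfer to another product. No such figure is warranted.

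**What to change.** Text changes only.

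1. In Section 5.4 and in Appendix A, Section 5, state that conservatism of normalised inhalation exposure has not been shown for fine sprays of other solvent base or vapour pressure, or for air-directed sprays, and that under-prediction cannot be ruled out for them. Carry the same statement with the database entry.
2. Beside Appendix A Tables 5 and 6, report the pilot residues per mg ADBAC dispensed, with the confounding and the air freshener's erratic output noted.
3. Do not draw the boundary at ethanol-containing products, which the pilot data do not support.

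Design, sample size and field conduct are unaffected. The cost is a narrower inhalation claim.

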2.2. Marquart et al. (2003)

This publication is a review of available literature on the subject and discusses various determinants influencing exposure and use of the information in developing models for risk assessment. Inhalation and dermal exposures are complex processes and determinants of exposure depend on exposure scenario. In the aerosol spraying process the most important exposure determinants are:

- Spray volume i.e., amount of liquid sprayed
- Area treated
- Orientation of worker in relation to application or orientation of the spray applicator
- Proximity of the worker to the source i.e., distance from the application surface
- Spray pressure is related to particle size distribution; and deposition velocity is important for both inhalation and dermal exposure from use of aerosols
- Type of surface
- Worker habits

The publication does not provide data that can be directly substituted for estimating inhalation and dermal exposure from use of aerosol products. However, the information available supports the arguments, made subsequently, for product selection in the proposed study and provides guidance in study design. In the proposed study the most influential determinants for inhalation and dermal exposure will be considered both in the selection of the product and study design.

2.3. Nazaroff et al. (2006)

This was an extensive study undertaken for the California Air Resources Board (ARB) to determine the exposure from air contaminants produced by indoor use of consumer products for cleaning and as air fresheners. The study focused on the volatile organic components that contributed to production of photochemical smog including indoor reactive chemistry. The main emphasis was on the terpene-ozone reaction.

The indoor household products were identified by a shelf survey of five retail outlets in Northern California and by literature review on air pollutants. The product list included disinfectants, general-purpose degreasers, general-purpose cleaners, wood cleaners, furniture maintenance products, spot removers, multi-purpose solvents and air fresheners. From the list, six products (one from each group) were selected to study emissions and concentrations of the primary constituents in simulated-use experiments in room-sized research chambers. Experiments were also conducted in a bench-scale chamber under controlled conditions to study the reactivity of volatiles with ozone. The test atmosphere was analyzed for various components and particle size distribution was measured only up to four micrometers for the aerosol products. The data was analyzed for its relevance to humans.

The study concluded that inhalation exposure to air pollutants can be expected to occur under some circumstances during the use of common household cleaning products. In this elaborate study on exposure to household products no effort was made to determine the concentration of the active ingredients in air and the focus was on the volatile liquids and gases. Therefore, the data is not directly applicable to estimate exposure to the aerosol products represented by the Task Force membership.

2.4. PHED and CMA Studies

These studies have been discussed in detail previously in the Scenario Design Document and will not be considered further.

2.5. Conclusions from the Existing Data

From the review of the relevant literature, it can be concluded:

- The existing information does provide useful general information on the behavior of the aerosol products and identifies variables which are most influential in defining inhalation and dermal exposure by use of aerosols.
- The data are very limited and do not fully represent the use patterns and exposure scenarios of the products represented by the Task Force and therefore, are not suitable for estimating the inhalation and /or dermal exposures by use of aerosol cans.
- The available knowledge could be helpful in the proposed study design and selection of the product.

The proposed study can be designed to provide exposure data most suitable for use in the risk assessment of the aerosol biocide products in cans.

2.6. Relevance of Existing Data to the Study Goals

As discussed above in the conclusions the data cannot be directly used to assess the inhalation or dermal exposure associated with use of pressurized aerosol cans, but has relevance in defining the parameters that contribute to and influence the degree of exposure. The main goal of the study is to generate data using a product with high exposure potential and covering the most influential variables associated with inhalation and dermal exposure. The data generated can then be used in risk assessments for most exposure scenarios resulting from use of aerosol cans.

2.6.1. Most Influential Variables Effecting Exposure

The most influential variables described in the existing data and relevant for the current study design and selection of the representative product (test material) are:

- Amount of material used
- Release rate
- Particle size distribution
 - o Nozzle technology
 - o Pressure in the can
 - o Temperature / humidity
- Surface on which product is used
- Orientation of the can during use

These influential variables are considered and discussed in more detail in the following section rationale for selection of the test substance for the study.

3.0 RATIONALE FOR SELECTION OF TEST SUBSTANCE

Test substance selection was based on the hypothesis that a representative product /products could be selected and data generated with the following characteristics:

- Serve as a surrogate for most pressurized aerosol use categories
- Use pattern represents high end exposure a conservative scenario
- Use scenario covers most influential variables of exposure
- Has a stable active ingredient with a low Limit of Quantification
- Results can be extrapolated to most antimicrobial aerosol products

In order to meet the above **criteria for product selection**, the following information was considered:

- 1. Survey of the products represented by the AEATF II
 - a. Product profile including aerosol characteristics, release rate, nozzle size and use scenarios
 - b. Consideration of influential variables
- 2. Identify product categories based on use scenarios
- 3. Conduct of a pilot/ method development study using a representative product from each category
- 4. Identify product to serve as surrogate to meet criteria for the study design and product selection

